#### *Semi-structured interviews*

Analysis will use the principles of the constant comparative method and interpretive thematic analysis. One member of the research team will lead a process of iterating between the developing analysis and new data, and other members of the research team will develop and test the analysis by periodic discussion. The analysis will be interpretive and consider both latent and manifest aspects of the data, thereby acknowledging both the manner that participants talk as well as the explicit content. Analysis will progress in parallel with recruitment and will end when theoretical saturation is reached. Systematic data coding will be performed; exceptional case analysis will be discussed within the research team; and data

will be triangulated with quantitative data from the PIM-COVID study to enriching findings and interpretation. Analysis will be assisted by qualitative analysis software.

### **3.6 Sample size**

There is no formal sample size required. Overall we aim to recruit until September 2022 or when 1000 patients have answered the questionnaire at all three time points, whichever occurs first. We will initially approach 20 intensive care units for participation. If necessary we will extend the number of recruiting units to facilitate reaching this recruitment target. We have factored in a 40% return rate, so we will have to send out 2500 questionnaires in order to achieve our target.

With the semi-structured interviews, based on previous experience of qualitative evaluation of psychological effects on patients, we anticipate theoretical saturation with about 40 participants.

## **4. Recruitment and Withdrawal of Participants**

### **4.1 Recruitment**

Recruitment will take place at hospitals across the UK, and be conducted by junior doctors who are either training, or have a specialist interest, in intensive care medicine; and/or allied health professionals working in intensive care (including Advanced Critical Care Practitioners). Therefore, recruitment will be balanced within the demands of the clinical workload. It is intended that all patients discharged from a recruiting ICU, that were admitted and treated for COVID-19, will be given an information sheet explaining the study to them and explaining the possibility of receiving three questionnaires during the year following discharge. Where this is not feasible, every reasonable effort will be made to contact these patients prior to hospital discharge. All ICUs with members in the Trainee Research in Intensive Care (TRIC) will be invited to participate.

For the semi-structured interviews, identification of participants will be performed by the central research team by accessing the PIM-COVID REDCap database. Where patients have agreed to be contacted by phone or email, these contact details will be available within the REDCap database. Patients who have provided consent to be contacted will be approached by telephone or email to discuss their potential participation in the study. A written information sheet will be sent via email or post as per participants' preferences. Participants have been asked whether or not they are happy to be contacted as part of the 3, 6 and 12 month questionnaires; participants who have indicated they would not like to be contacted will not be approached.

#### **4.2 Inclusion criteria**

1. Adult patients  $\geq 18$  years
2. Survival to intensive care / high dependency unit discharge following an admission of  $\geq 24$  hours
3. Treated for COVID-19

#### **4.3 Exclusion criteria**

1. Unable to complete questionnaires
2. Unable or unwilling to consent
3. Unable to speak, understand or communicate in English
4. Patients with diagnosed, pre-existing cognitive impairment (at the time of ICU admission)
5. Patients without a fixed abode, at which postal questionnaires might be received, and who have no access to a personal email address.

#### **4.4 Criteria for Premature Withdrawal**

A patient may request to be withdrawn from the study at any time, for any reason, without prejudice and without an impact on their clinical care. A patient may also be withdrawn from the study at the request of his/her legal representative or clinical team, for any reason.

### **5. Study Procedures**

#### **5.1 Screening Procedures**

All patients discharged from the ICU will be screened against inclusion and exclusion criteria prior to enrolment. A screening and enrolment log will be kept with site files and will be archived following the end of the study (see section 7.3).

For the semi-structured interviews, a purposive sample of about 40 participants will be selected aiming for a sample that is diverse, representative of the cohort (in terms of ethnicity, sex, geographical location, degree of deprivation based on postcode, length of stay in ICU, etc), and inclusive of participants with and without evidence of psychological distress, based on answers to the 3 and 6 month questionnaires.

#### **5.2 Consent, Enrolment and Participant Follow-up Procedures**

On ICU discharge, where possible, patients will be provided with an information sheet outlining the study. A member of the research team with a valid GCP certificate will provide verbal information about the

study and answer any questions. Patients will be given the option to opt out of the study at this point, and thenceforth. Patients will also be given the option to opt in and be contacted by phone, email and/or post. Even if a patient opts in, and provides their contact details, they can choose to not participate in the study, and when they receive the invitation to participate in the first survey they can actively decline to participate or just not respond to the invitation. If the patient indicates that they do not wish to participate, they will be withdrawn from the study. If they do not indicate that they do not want to be contacted, and do not reply to the first survey, they will still be sent subsequent surveys and invited to participate in those. Critically ill patients often have impaired capacity as a result of their underlying illness and/or sedating medications, but usually regain capacity prior to being discharged home. It is important that only patients with capacity participate in the study. A patient will only be provided with an information leaflet in hospital once they have regained capacity. If a patient has not been given an information leaflet prior to being discharged home, they will be sent an information sheet by post along with an invitation to participate. If after receiving the information sheet and unique login details, the patient has not yet indicated via the REDCap database that they either consent to participating in the study or decline to participate, they will be contacted by telephone by the study team (unless they have previously opted out of being contacted by phone). There are three possible outcomes of this telephone contact: i) the patient consents to participating in the study; ii) the patient asks to be contacted again for re-discussion of consent; iii) the patient declines to participate in the study. There are three methods for patients to provide their consent, via i) an online consent form in the REDCap database; ii) witnessed telephone consent; iii) a written consent form, which the patient can request. Verbal agreement to participate in the study will be obtained by a member of the study team and will be recorded in the patient notes. Verbal agreement must be witnessed by another member of the site study team or site medical staff. The patient may withdraw consent at any stage. Upon withdrawing their consent, a study participant will be given the option for i) any previously collected data to still be included in the data analysis; or ii) all of their data to be removed from the REDCap database, and as such none of their data to be included in the analysis.

Where patients consent to taking part in the study using the online consent form, they will be asked to enter their name and email address, and whether they are happy to be contacted by email, post and/or phone. If patients decide not to provide an email address or their name, the study team will still be able to identify which patient has responded as the link to that consent form is unique to the patient and the REDCap record identifier can be cross referenced with the screening log. Where patients do not consent to taking part in the study, no personal information will be requested.

Eligible patients, who have not already opted out, will be invited to participate in an online questionnaire at 3, 6 and 12 months following discharge from ICU, or alternatively a paper copy of the questionnaire can be sent to them at the relevant time points or they may choose to answer the questionnaire over the phone with a member of the study team documenting their responses on REDCap. Prior to patient contact, electronic healthcare records will be accessed, and/or contact made with the patient's registered general practitioner, to confirm the patient's survival status. This is intended as a pre-contact check to minimise distress caused to families/relatives by making contact in the event a patient has died following discharge from the ICU.

For patients who have provided their email address, an email will be sent at 3, 6 and 12 months with a unique link to their survey. The link to their survey at each timepoint will expire after 1 month. At the beginning of the questionnaire, the study information will be repeated. Patients will be able to leave the study by contacting their local study team at any point during the study. If patients indicate they would prefer to complete a paper version, they will be provided with a pre-paid envelope to return their completed questionnaire. If patients indicate they would like to complete their questionnaire over the phone, this can be arranged with a study team member.

No patient identifiable information will be entered into REDCap prior to gaining patient consent. Patient information that is analysed will be pseudo-anonymised and each patient will have a unique study identifier assigned for use in REDCap. When the patient consents to be part of the study, their name and email address where provided will be stored in the REDCap database. Only the local study team will have access to this. The REDCap database will be used for the study duration and closed when all data has been acquired. Patient contact details will be kept during the study period only and will not be stored on the REDCap database without the patient's consent. In the event that the patient dies after having consented to participating in the study, then they will remain in the study and their data will be included in the final analysis.

#### *Semi-structured interviews*

At the end of the 3, 6 and 12 month questionnaires there is a question asking if we can contact participants for feedback about the questionnaires. For the semi-structured interviews, we will approach patients (by phone or email) who have indicated that they agree to being contacted, and invite them to participate in interviews to provide further information about their experiences after ICU discharge. Participants will be invited to take part in an interview, at around 12 months after discharge from intensive care. A written

patient information sheet will be provided by email or post, and consent to participate can be provided verbally or in writing.

Using open-ended questions we will explore physical and psychological consequences patients may face during their recovery phase; including physical sequelae such as loss of smell, breathlessness, fatigue, and psychological issues such as isolation, anxiety, flashbacks, or sleeping problems. We would like to learn about the follow-up services offered to participants by their GPs, the hospital and patient support groups, whether they chose to engage with services offered and how the support available influenced their way of coping. We also plan to explore what aspects of their recovery and any support they received they considered beneficial, and what aspects they felt could have been improved. The patient will be invited to share their experience without interruption, and only where topics of interest have not been covered, the Interview Guide (Appendix 7) will be used to provide prompts.

The interviews will be conducted by a medically qualified research fellow trained in conducting qualitative interviews, over the telephone, online (via a secure platform such as MS Teams or Zoom) or in person, to ensure equitable access for prospective study participants. Interviews will be audio recorded, anonymised and transcribed. Recordings will be held in accordance with GDPR regulations. Should patients become distressed during the interview, the one-on-one nature of the interviews should provide the opportunity for the interview to be postponed and to advise on additional support offered by locally available follow-up services, ICUsteps or other local support groups or their GP. Where patients describe psychological distress, a letter will be written to their GP and a copy sent to the patient, outlining what the patient has reported in the interview. We also have psychological support available within our study team to support patients who experience distress whilst recalling their experiences.

#### *Survey of Follow-up Services*

All intensive care units within the UK will be approached via email and invited to complete an online survey about follow-up services available for patients having been discharged from hospital after critical illness (See Appendix 7). ICUs will be contacted via the clinical ICU directors and through study teams, where sites are already involved in the PIM-COVID study. Invitations and information about the survey will be distributed through research network mailing lists and cascaded via social media.

#### *Survey of Study Team Members*

Study team members at all PIM-COVID sites will be invited to complete an online survey, which will explore the following:

- Socio-demographic characteristics of study team members
- Previous academic experience
- Feedback on involvement in the PIM-COVID study
- Attitudes towards health research
- Barriers and motivators to contributing to health research
- Future research plans

Questions evaluating participants attitudes, opinions and subjective feedback will be answered using a 5-point Likert scale. (See Appendix 8)

### **5.3 Schedule of study procedure**

Following screening and enrolment after ICU discharge, the following will be collected:

#### **Patient data from medical records:**

1. Age
2. Gender
3. Laboratory diagnosis of COVID-19
4. Physical health co-morbidities
5. Mental health comorbidities
6. Socioeconomic status (deprivation index calculated from postcode)

#### **Patient data from self-reported questionnaire:**

1. Highest educational level obtained (first questionnaire only)
2. Prior and current experience of, and treatment for, mental health difficulties
3. Current employment status

#### **ICU-acquired data:**

1. ICU date of discharge
2. ICU length of stay \*
3. APACHE II score
4. Mechanical ventilation received \*\*
5. Delirium during ICU admission \*\*\*
6. Benzodiazepine requirement during ICU admission

\* Defined as the length of stay recorded on the ICNARC database

\*\* Defined as invasive mechanical ventilation via an endotracheal tube or tracheostomy using PEEP  $\geq$  5cmH2O

\*\*\* Defined as present if recorded in the medical notes during ICU admission or discharge

#### **Psychological assessment via self-reported questionnaire:**

The following four self-report questionnaires will be administered at 3, 6 and 12 months following ICU discharge:

1. HADS
2. IES-6
3. CAS-1R
4. EQ-5D-5L

#### **Semi-structured interviews:**

The interview guide that will be used to help conduct the interviews is outlined in Appendix 7.

#### **Survey of Follow-up Services:**

The survey questions are outlined in Appendix 8.

#### **Survey of study team members:**

The survey questions are outlined in Appendix 9.

#### **5.4 Accessing locally held data**

Where possible, locally collected data that contributes to the ICNARC database will be used rather than directly accessing patient notes. Accessing this data minimises error and bias in this study. Prior to study commencement, an agreement will be sought to access ICNARC data. Where additional information may be made available through large existing databases, including but not limited to ISARIC-CCP and GenOMICC, application will be made for data linkage and the necessary permissions sought.

#### **5.5 Missing observations**

Every effort will be made to minimise missing baseline and outcome data in this study. Reasonable efforts will be made to obtain complete datasets. Where this is not possible, data will be reported as missing in the presentation of the results. In the event that participants are non-responders to the 3- and 6-month questionnaires, the 12-month questionnaire will still be sent to participants (unless consent has previously

been withdrawn). This will be accompanied by a telephone call to confirm the patient's willingness to continue as a study participant.

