## 1. Study Summary

Title	The psychological impact of surviving an intensive care admission due to coronavirus disease 2019 (COVID-19) on patients in the United Kingdom
Protocol short title / Acronym	Psychological Impact of COVID-19 on Intensive Care Survivors / PIM-COVID
Protocol Version number and Date	Version: 1.6 8 April 2022
IRAS	282400
Is the study a Pilot?	No
Study Duration	24 months
Methodology / Study Design	Mixed methods: multicentre longitudinal observational study, longitudinal semi-structured interviews and observational structured survey.
Sponsor	Liverpool University Hospitals NHS Foundation Trust
Co-Chief Investigators	[name] [name]
Medical conditions under investigation	1) Anxiety, 2) depression and 3) trauma symptoms
Purpose of study	To assess the short- and long-term psychological impact on patients who have survived an admission to intensive care due to COVID-19, and identify possible predictors of anxiety, depression and trauma symptoms in this patient group.
Primary objective	To identify the proportion of patients surviving an admission to intensive care due to COVID-19 who experience anxiety, depression and/or trauma symptoms in the 6 months post-discharge, assessed using the Hospital Anxiety and Depression Scale (HADS) and the Impact of Event Scale-6 (IES-6), respectively.
Secondary objectives	
 
Identify demographic, clinical, physical and/or psychosocial predictors of depression, anxiety and/or trauma symptoms at 3-, 6- and 12-months post discharge from ICU.
 

	
 
2. Assess the feasibility of using a self-reported online questionnaire to assess anxiety, depression and/or trauma symptoms in patients following ICU admission.
 
3. Explore the experiences of critical care survivors following COVID-19 infection during their recovery phase, including perceptions about the care received and support available to them, using semi-structured interviews
 
4. Assess geographical differences in the availability and structure of follow-up services offered to patients with critical COVID-19 after hospital discharge.
 
5. Gain feedback from the study team members on their involvement in the study.
 

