#### **3.2 Study Objectives**

##### **Primary objective:**

To identify the proportion of patients who survive ICU admission following treatment for COVID-19 that experience anxiety, depression and/or trauma symptoms at 6 months, assessed using the Hospital Anxiety and Depression Scale (HADS) and the Impact of Event Scale-6 (IES-6), respectively.

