### **3.5 Study Statistics**

This study is planned as a descriptive study in an effort to quantify the psychological impact on ICU survivors of COVID-19. It is anticipated that the study will report its findings using descriptive methods in the absence of a comparator group.

Trajectories of anxiety, depression, and trauma symptoms will be estimated using growth curve analysis. To improve power, we will use the full range of anxiety, depression and trauma symptom scores (not cut-off scores). Growth modelling is latent variable covariance modelling to estimate the intercept (value of the initial observation) and slope (the rate of change from this observation over time) of a time series of mean scores. We will estimate full sample single class models (eg, assuming homogeneity across the sample) for each outcome. Initial fixed parameters will be; error variance constrained to equality across observations, mean intercept and slope constrained to zero, intercept and slope constrained to equality, and intercept and slope covariance constrained to zero. Parameters will be systematically relaxed in that order until good fitting models ( $CFI > .95$ ,  $RMSEA < .05$ ) are identified with maximum fixed parameters. Linear and quadratic slope models will be tested; linear models being defined as slope parameters 0, 1, 4, and 12 and quadratic slopes as 0, 1, 8 and 24.

We will estimate and predict individual survivors' slope and intercept scores. Scores will be calculated using the regression method, setting intercepts for observed variables to 0 and imposing equality of variance. We will then regress predictor variables onto intercept and slope scores for all outcomes to identify variables likely to determine trajectories of anxiety, depression and trauma symptoms.

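### As written, the primary 6-month proportions are in effect unadjusted responder proportions; scores from the other waves could reduce any bias cheaply

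*Combined protocol and SAP*

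**What the plan says.** The primary objective in section 3.2 is the proportion of survivors who "experience anxiety, depression and/or trauma symptoms at 6 months". The Study Summary words the same objective as "trauma symptoms in the 6 months post-discharge". Section 3.3 defines anxiety and depression caseness as a HADS subscale score of 8 or more.

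Section 3.5 expects that "the study will report its findings using descriptive methods in the absence of a comparator group". For the growth curves it says "we will use the full range of anxiety, depression and trauma symptom scores (not cut-off scores".

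On missing data, section 5.5 promises reasonable efforts to complete the dataset and then gives one rule: "Where this is not possible, data will be reported as missing in the presentation of the results". It also keeps sending the 12-month questionnaire to people who missed earlier ones. Section 5.2 has a matching rule for people who do not answer the first survey: "they will still be sent subsequent surveys and invited to participate in those".

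HADS and IES-6 are collected at 3, 6 and 12 months (section 5.3). Demographic, comorbidity, deprivation and ICU variables are also recorded there. Recruitment rate, retention and missing key data are feasibility outcomes (section 3.3), and sites keep a screening log (section 5.1).

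**The concern.** In a descriptive study with no comparator, the proportion is the main result. The Introduction says it is needed to tell services how many survivors are affected. No section says who is in its denominator, and the only rule for a missing 6-month questionnaire is to show that it is missing. An analyst following the plan would divide 6-month cases by 6-month responders.

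That is unbiased for consented participants only if those who miss the 6-month questionnaire have the same prevalence as those who return it. Psychological symptoms could plausibly make people less likely to reply, or more likely. A larger sample does not reduce such a bias. Many of the people concerned may have answered the same scales at 3 or 12 months, and the plan makes no use of those answers for this estimate.

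**Working it through.** **Does another part of the plan supply the estimate?** The growth models describe trajectories of continuous scores, with no stated missing-data estimator and no step from scores to caseness. The feasibility outcomes display non-response but do not adjust for it. The proportion therefore rests on section 5.5 alone.

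**The plan's own figure.** Section 3.6 says "We have factored in a 40% return rate" and derives 2500 questionnaires: 1000 / 0.40 = 2500, which reproduces. It does not say whether 40% is per mailing or for all three waves. It concerns questionnaires sent, not consented participants, so it is not the 6-month reply rate needed below.

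**Size of a possible bias among consented participants.** Let r be the share who reply at 6 months, and D the prevalence in repliers minus that in non-repliers. The bias of the responder proportion is (1 − r) × D. Both inputs are assumed, because the documents give neither.

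| r | D = 5 points | D = 10 points | D = 15 points |
|---|---|---|---|
| 80% | 0.20 × 5 = 1 | 0.20 × 10 = 2 | 0.20 × 15 = 3 |
| 60% | 0.40 × 5 = 2 | 0.40 × 10 = 4 | 0.40 × 15 = 6 |
| 40% | 0.60 × 5 = 3 | 0.60 × 10 = 6 | 0.60 × 15 = 9 |

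The sign follows D and may be either. For scale, take 34% prevalence, borrowed from the Introduction's 12–14-month figures, and n = 1000. The 95% half-width is 1.96 × √(0.34 × 0.66 / 1000) = 2.9 points.

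**Would the other-wave scores help?** A simulation of 200,000 consented participants per scenario used three equally correlated normal scores with 34% cases at 6 months. All held a 3-month score and 70% a 12-month score. Missing 6-month scores were drawn from a regression on the scores held. Every input is assumed, and reply was made to fall as symptoms rise.

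- Reply depends on the 3-month score (correlation 0.5 to 0.8, reply 60% or 80%, log-odds falling 0.3 to 0.8 per SD): the responder proportion is 25.6% to 32.9%. The imputed proportion is 33.7% to 34.2%, within 0.2 points of the simulated truth.
- Reply depends on the unseen 6-month score (log-odds falling 0.5 per SD, reply 70%): the responder proportion is 28.4%. The imputed proportion is 29.9%, 31.3% and 32.0% at correlations 0.5, 0.7 and 0.8, against truths of 33.8%, 33.9% and 33.9%. Bias removed is 1.5/5.4 = 28%, 2.9/5.5 = 53% and 3.6/5.5 = 65%.

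These shares would be smaller where other-wave scores are missing too.

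**The two wordings of the objective.** Suppose the Study Summary means a case at 3 or at 6 months, with prevalence 34% at each and correlation φ between the two binary states. Then P(either) = 2 × 0.34 − [0.34² + φ × 0.34 × 0.66]. For φ = 0.6 this is 0.68 − 0.2502 = 43.0%; for φ = 0.7 and 0.4 it is 40.7% and 47.5%. Section 3.2 would give 34%.

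**The case against.** The study is declared descriptive, and its conduct works against non-response: telephone contact, three ways to answer, continued invitations, a call with the 12-month questionnaire, and published retention and missing-data rates. Missing data must be reported, so readers should be able to see how many people lie behind the proportion. All of that stands. It lowers and displays non-response, but it neither defines the denominator nor adjusts the estimate.

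Several stronger readings are tempting and are not supported.

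- A reader might infer that the primary result will be confined to people who answered every wave, because section 3.6 recruits until September 2022 or "when 1000 patients have answered the questionnaire at all three time points". That is a recruitment stopping rule; nothing makes it an analysis set.
- A reader might infer that withdrawals and deaths are unhandled. Section 5.2 excludes people who ask for their data to be removed, and requires a survival check before contact. It keeps the data of participants who die after consenting. What is unstated is only how deaths before 6 months enter the 6-month proportion.
- A reader might infer from the 40% return that the result is known to be badly biased. The documents give no prevalence in non-responders, so they establish neither size nor direction.

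It is also fair that multiple imputation is one choice among several, and that patients who never consent may be the larger loss. Imputation does nothing for them.

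**Conclusion.** The point holds as a worthwhile, cheap improvement, not as a demonstrated error in the result. As written, the 6-month proportions default to unadjusted proportions among responders. Whether that biases them depends on a difference between consented repliers and non-repliers that the documents do not give. Under the assumed inputs above, the bias is 1 to 9 points in either direction, the same order as the sampling half-width or larger.

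Imputation from the other waves rests on data being missing at random given the observed scores and covariates. Where reply depends on the unseen 6-month score, it should be expected to remove only part of the bias. The simulated shares illustrate this and should not be quoted as a forecast for this study. The conclusion covers consented participants only.

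**What to change.** Add to section 5.5:

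> The 6-month proportions will be estimated for all participants who consent at any wave and were alive at 6 months, including those who first consent after 6 months, and excluding those who asked for their data to be removed (section 5.2). Deaths before 6 months are reported separately. Missing 6-month HADS and IES-6 scores will be multiply imputed from the 3- and 12-month scores and the recorded demographic, comorbidity, deprivation and ICU variables, and caseness derived from the imputed scores. The 6-month responders-only proportion and its n will be shown alongside, with a sensitivity analysis shifting the assumed prevalence among consented 6-month non-responders up and down.

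Late consenters must be included. A rule requiring consent by the 6-month wave would keep someone who first consents by answering at 6 months, yet drop a 6-month non-responder who consents at 12 months. That selects on response.

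Also:

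- Reconcile the Study Summary with section 3.2 on whether the proportion is over the first 6 months or at 6 months.
- State the IES-6 cut-off, which section 3.3 does not give.
- For eligible patients who never consent, report their number from the screening log and claim no correction.

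The cost is some extra analysis of data already being collected, slightly wider intervals and an explicit missing-at-random assumption. No new contact with patients is needed.
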